5.1 Sample Size

Assuming a true proportion of 54% clinically cured in the treated group a sample size of 24 patients is needed to obtain 80% power to show that the one-sided 95% confidence interval (CI) for the clinical cure rate is above 30%. To compensate for patients with missing data a total of 26 patients will be included.

Statistical Analysis Plan

Study ID: CL4

6 Assessments

An overview of the assessments performed during the study are presented in Table 1.

Table 1. Schedule of assessments and procedures

Evaluations	Day 0	Day 0-5	Day 6	Day 7 (+2 days)	Day 11 (±1 day)	Day 14 a (±2 days)	Day 25 (±3 days)
	Screening	Treatment	Follow-up	Follow-up	Follow-up	Follow-up	Follow-up
	Visit 1		At home	Visit 2	At home	Visit 3	Visit 4 (Telephone)
Informed consent	X						
Demography	X						
Eligibility criteria	X						
Pregnancy test (urinary)	X						
Medical and surgical history	X						
Prior and concomitant medications	X			X		X	X
Menstruation (date of end/onset)	X			X		X	X
Gynaecological examination incl. CVVS	X			X		X	
Vulvovaginal symptoms (via patient questionnaire or telephone)		X	X		X		X
Fungal microscopy assessment	X			X		X	
Vaginal swab for culture ^b	X			X		X	X
Vaginal swab for sequencing ^b	X			X		X	X
Treatment dispensing	X						
Treatment with Gedea Pessary ^c		X (Daily)					
Vaginal pH (pH strip test)	X			X			
Patient questionnaire/Usability			X				
AEs				X		X	X
Product accountability ^d				X			
Rescue treatment				X ^e		X ^e	X ^f

^a Only for patients with no clinical and mycological cure Day 7.

^b Self-swab on Day 25(presence of Candida + sequencing analysis of the vaginal microbiome).

^c Treatment to be self-administered by the patient at home, at night before going to bed.

^d Patients should be asked to return all used and not used treatment packages.

^e Offered if the VVC symptom score on that day is equal to or higher than the score at the inclusion visit (Day 0).

^f If symptoms recur on Day 25, or symptoms persist, rescue medication could be offered according to standard clinical practice.

Statistical Analysis Plan

Study ID: CL4

6.1 Demography and baseline characteristics

Demographic information will be collected at Screening (Day 0) and will include initials, sex, birth date and ethnic origin (Caucasian, Asian or Pacific Islander, African descent, Mixed/multi-racial, or other).

All study patients will perform a pregnancy test (urine dipstick) at Screening (Day 0). Pregnancy is an exclusion criterion. If pregnancy is confirmed in a patient during the study, the patient will be withdrawn, and the pregnancy will be followed.

The Investigator or delegatee will ask about onset and end of last menstruation on the Day 0 visit, and ask for possible menstruation onset on Day 7, Day 14 and Day 25. Intermittent bleeding should also be possible to register in the eCRF as AE.

6.2 Prior and concomitant medications

Information about any concomitant medication, including OTC medications and vitamins used by patients within 14 days prior to inclusion and during the study, will be collected at all site visits for all patients and also at the telephone contacts. The generic name or trade name, dosage and reason for use shall be recorded in the eCRF for all medications.

6.2.1 Rescue medication

On Days 7 and 14, patients having VVC symptoms of the same or higher intensity compared to the inclusion visit (Day 0), will be offered rescue treatment, if considered necessary. Rescue treatment will be according to standard clinical routines, as described below. Any rescue treatment will be administered after all assessments have been completed during the visit.

Patients will receive a prescription of fluconazole (50 mg as a single dose, orally) or clotrimazole pessary (500 mg as a single dose, intra-vaginally) and if necessary, topical treatment with 1% clotrimazole or 1% clotrimazole/1% hydrocortisone.

In addition, patients with recurrence or persistent symptoms on Day 25 (i.e., symptoms recurred on Day 25) may also be offered rescue treatment, according to the standard clinical routines mentioned above. The site will decide whether a visit to the clinic is needed and if rescue medication should be prescribed.

Patients taking rescue medications prior to the visit where clinical cure is assessed (Day 7 or Day 14), will be considered in the statistical analysis as described in Section 7.9.1.

The use of any rescue medication will be recorded in the eCRF.

6.2.2 Restrictions

During the study, the following medications are not allowed and should be avoided:

1. Anti-fungal medication related to VVC – explicitly anatomical therapeutic chemical (ATC) codes J02A and D01AC.
2. Other treatments for VVC (e.g. probiotics like Candicur and Multigyn).

Since use of concomitant anti-fungal therapy or other treatments related to VVC due to lack of efficacy prior to CVVS evaluation used for the primary endpoint definition is considered an intercurrent event, a review of all concomitant medication will be performed prior to data base lock to classify the concomitant medication as an intercurrent event or not.

6.3 Medical and surgical history

6.4 Gynaecological examination

Patients will undergo a gynaecological examination by the Investigator or an authorised designee at the site visits (on Day 0, Day 7 and Day 14), in order to assess:

- Vulvovaginal symptoms (itching, burning, and irritation) will be assessed by patients themselves according to a scoring scale (0-3) as per the patient questionnaire, on Days 0 to 6, Day 11 and Day 25 (see Section 6.5.1). On Day 0, 7 and 14 the investigator will ask the patient regarding the vulvovaginal symptoms and record this in the eCRF.

Statistical Analysis Plan

Study ID: CL4

- Vulvovaginal signs (erythema, oedema and excoriation) will be assessed by the Investigator or authorised designee on Day 0, Day 7 and Day 14
- VVC diagnosis (assessed by the Investigator or designee): The diagnosis is based on CVVS score and microscopic analysis of a KOH or saline preparation, during the site visits (Day 0, Day 7 and Day 14). The assessments will be recorded in the eCRF. The diagnosis criteria are the following.
 - Having a white or creamy vaginal discharge
 - At least 2 of the following signs and symptoms of VVC that are characterised as at least moderate1: itching, burning, irritation, oedema, erythema, or excoriation.
 - KOH or saline preparation from the inflamed vaginal mucosa or secretions revealing yeast forms (hyphae or pseudohyphae) or budding yeasts.

For definition of clinical cure see Section 3.1.1.

6.5 Patient questionnaire

Questions will be asked directly in the electronic patient reported outcomes (ePRO) system via mobile phone or computer (ViedocMe™). Patient initiated ViedocMe forms will be tied to the same study day as it was initiated. However, forms that are initiated during the period 00:00 to 04:00 will be tied to the previous study day. In case of multiple assessments during the same study day (while also taking the mandatory forms into account), the first non-missing assessment will be used in analyses and summaries. If there are proofs like e-mail communication, or other proofs that a patient initiated form, initiated later, belongs to a previous day, this may be accepted.

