Appendix 1 Patient Questionnaire

Questions will be asked directly in the electronic patient reported outcomes (ePRO) system mobile application ViedocMe™.

Section 1. Vaginal candidiasis symptoms and pessary administration

Pessary administration:

At Days 0 to 5, the patient should confirm that they have administered the pessary:

Question on treatment days:

Have you applied the pessary?

- Yes
- No

If no, please provide reason: (free text).

Scoring of vulvovaginal candidiasis symptoms:

The vulvovaginal candidiasis (VVC) symptoms will be rated by all patients on Days 0 to 6 , Day 11 and Day 25.

The VVC symptoms will be rated according to 0-3 scale, as shown below.

	0 = none (absent)	1 = mild (slight)	2 = moderate (definitely present)	3 = severe (marked, intense)
Irritation				
Itching				
Burning				

Section 2. Usability

All patient should reply to the following questions on Day 6.

Questions – Day 6

1. Is the vaginal pessary easy to use?

- Yes
- No

If no, provide reason: (free text).

2. Did all pessaries remain in the vagina during treatment?

- Yes
- No

(if No) 2a. During how many dose administrations did you experience that the pessary did not remain in the vagina?

- Once
- 2-3
- 4-5
- All

2b. When the pessary does not remain, how would you describe what most frequently is happening?

- Just small pieces are falling out
- Large pieces are falling out

Please specify after how long time they generally falls out.

- Within 12 hours
- Between 12-24 hours after administration
- More than 24 hours after administration

- The whole pessary is falling out

Please specify after how long time it falls out.

- Within 12 hours
- Between 12-24 hours after administration
- More than 24 hours after administration

3. How do you generally regard the treatment?

1	2	3	4	5	6	7	8	9	10
---	---	---	---	---	---	---	---	---	----

Not satisfied

Very satisfied

Section 3. Reminders

Patients will receive the following reminders and questions via the mobile application:

- **Administration**

Reminder about administration of the investigational product on Days 0 to 5 and VVC symptom scoring on Days 0 to 6, Day 11 and Day 25.

The investigational product is to be self-administered at night before going to bed.

Please score your vulvovaginal symptoms.

•

- **Sampling reminder and questions at Day 25**

1. Have both vaginal swab samples been taken?

- Yes
- No

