6.5.1 Vaginal candidiasis symptoms and pessary administration

The following information will be collected in the ePRO system.

Pessary administration:

At Days 0 to 5, the patient should confirm that they have administered the pessary:

Question on treatment days:

Have you applied the pessary?

- Yes
- No

If no, please provide reason: (free text).

Scoring of vulvovaginal candidiasis symptoms:

The vulvovaginal candidiasis (VVC) symptoms will be rated by all patients on Days 0 to 6, Day 11 and Day 25.

The VVC symptoms will be rated according to 0-3 scale, as shown below.

	0 = none (absent)	1 = mild (slight)	2 = moderate (definitely present)	3 = severe (marked, intense)
Itching				
Burning				
Irritation				

Statistical Analysis Plan

Study ID: CL4

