8.3 Compliance

Two separate calculations will be used to derive compliance (%).

Patient reported compliance will be calculated as $100 \times$ the number of ordinary study days (0 to 5) the patient responded yes to the question 'Did you apply the pessary' divided by 6.

Statistical Analysis Plan

Study ID: CL4

Pessary kit derived compliance will be calculated as $100 \times 6 \times (\text{number of pessary kit returned} - \text{number of pessaries lost} - \text{number of returned unused pessaries})$ to the clinic divided by 6. Note that this definition implies non-compliance in case of failure to bring back kits to the clinic.

Total study compliance will subsequently be derived as the maximum of patient reported compliance and pessary kit compliance.

References

- [1] ICH Harmonised Tripartite Guideline for Statistical Principles for Clinical Trials E9. February 1998.
- [2] ICH Harmonised Tripartite Guideline for Structure and Content of Clinical Trial Reports E3. November 1995.

Statistical Analysis Plan

Study ID: CL4

9 Signoff

We have read this SAP for the CL4 study and confirm that, to the best of our knowledge, the statistical analyses to be performed in this study are accurately described.

Gedea Biotech AB: *NAME*

SIGNATURE AND DATE

DocuSigned by:

NAME

Signing Time: 25-mar-2024 | 18:30 CET

C021A0A7C87E410FBDBF942B730DA13A

CTC SAP Author / Approver: *NAME*

SIGNATURE AND DATE

DocuSigned by:

NAME

Signing Time: 25-mar-2024 | 18:28 CET

A1F9A57C0B42488887FD67733546F97B

Certifikat om färdigställande

Kuvert-ID: 5B2C2F63C7CE46AA99443AA0722A11DA

Status: Färdigställda

Ämne: Complete with DocuSign: Statistical Analysis Plan, GED004 CL4 FINAL v2.0 25MAR2024.docx

Källkuvert:

Dokumentsidor: 21

Signaturer: 2

Kuvertskapare:

Certifikatsidor: 5

Initialer: 0

NAME

AutoNav: Aktiverat

[name]

Kuverterad stämppling: Inaktiverat

37

Tidszon: (UTC+01:00) Amsterdam, Berlin, Bern, Rome, Stockholm, Vienna

NAME

IP-adress:

Spela in spårning

Status: Original

Hållare: NAME

Plats: DocuSign

25-mar-2024 | 18:27

Signeringshändelser**Signatur****Tidsstämpel**

NAME

NAME

Skickade: 25-mar-2024 | 18:28

Clinical Trial Consultants, CTC AB

Signaturantagande: Förvald stil

Visade: 25-mar-2024 | 18:28

Säkerhetsnivå: E-post, Kontoautentisering
(obligatoriskt)

Signatur-ID:

Signerade: 25-mar-2024 | 18:28

-

Med IP-adress:

Med signeringssautentisering via DocuSign-lösenord

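### SAP 6.5 keeps the first app form of each study day for every item, so an early No on pessary use outlasts a later Yes, and some next-morning forms land on the wrong day

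*SAP*

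**What the plan says.** SAP 6.5 sets both the dating and the selection of app forms.

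- Dating: "Patient initiated ViedocMe forms will be tied to the same study day as it was initiated", except that "forms that are initiated during the period 00:00 to 04:00 will be tied to the previous study day".
- Re-dating: where there is e-mail correspondence "or other proofs that a patient initiated form, initiated later, belongs to a previous day, this may be accepted".
- Selection when a study day has more than one form: "the first non-missing assessment will be used in analyses and summaries". No item is exempted.

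SAP 6.5.1 puts two kinds of item in the same part of the questionnaire: the three symptom scores and a Yes/No application question ("At Days 0 to 5, the patient should confirm that they have administered the pessary"). On timing, Protocol Appendix 1 says: "The investigational product is to be self-administered at night before going to bed".

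SAP 8.3 bases patient-reported compliance on "the number of ordinary study days (0 to 5) the patient responded yes to the question", divided by 6. It adds a kit-derived figure, which counts an unreturned kit as non-compliance, and defines total compliance as the larger of the two.

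**The concern.** A first-non-missing rule suits an item whose first answer is as valid as its later ones. The application question is different. Before a bedtime dose the true answer is No, and after it the true answer is Yes. When a woman answers twice in one evening, the rule keeps the superseded answer.

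The dating rule foresees late entry but stops at 04:00. A woman who falls asleep after insertion and starts a form on waking has it tied to the new day. Being first, it also takes the place of that evening's symptom scores.

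At stake are the patient-reported compliance figure and the daily symptom-sum endpoints (6 and 7). Protocol 7.6 names only the app question and vaginal pH as compliance measures. Protocol 5.2 treats speed of relief as a central property of a treatment for this condition and wants it for timing rescue in a later study.

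**Working it through.** The plan gives no figure on this point, so the check applies the written rules to form sequences and then computes compliance.

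**Inputs**
- Dating and selection rules: SAP 6.5.
- Bedtime dosing on Days 0–5: Protocol 7.2.5 and Appendix 1.
- Patient-reported compliance = 100 × (days with Yes) / 6: SAP 8.3.
- Kit-derived compliance as printed = 100 × 6 × (kits returned − pessaries lost − pessaries returned unused) / 6; total = maximum of the two: SAP 8.3.
- Planned number of women: 26.
- Clock times below are illustrations. The documents give no reminder times.

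**Step 1. Apply SAP 6.5** (next-morning forms are patient-initiated, with no accepted proof)

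| Forms | Result |
|---|---|
| Day 1 at 18:00 No; Day 1 at 23:00 Yes | Day 1 stays No |
| Day 1 dose reported on Day 2 at 08:00; Day 2 form at 23:00 | Both fall on Day 2; the 08:00 form is kept, the evening score is dropped, Day 1 is empty |
| Same, but first form at 02:00 | Dated to Day 1; both days correct |
| Day 5 dose reported on Day 6 at 08:00; Day 6 form at 22:00 | Day 5 has no Yes, Day 6 is not counted in SAP 8.3, and the Day 6 evening score is dropped |
| All six doses reported at 08:00 the next morning | Days 1–5 hold a Yes, Day 0 is empty, Day 6 is not counted: 5/6 |

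The last row matters for size: an unbroken run of late forms costs one dosing day, not six.

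**Step 2. Patient-reported compliance**
- One dosing day lost: 100/6 = 16.7 points.
- One, two or three days lost from a true 6/6: 5/6 = 83.3%, 4/6 = 66.7%, 3/6 = 50.0%.
- Effect of one lost day on the mean over 26 women: 16.7/26 = 0.6 points.

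**Step 3. Total compliance**
- Kit returned, none lost or unused: 100 × 6 × (1 − 0 − 0)/6 = 100%. The maximum is 100% whatever the app says.
- Kit not returned: 100 × 6 × 0/6 = 0%. Total equals the patient-reported figure, so 83.3%, 66.7% or 50.0% in the cases above.
- Five doses applied, one pessary lost, kit returned (true value 5/6 = 83.3%), one true Yes held at No: patient-reported 4/6 = 66.7%. The kit formula as printed gives 100 × 6 × (1 − 1)/6 = 0%, so total is 66.7%. If the formula is meant as six pessaries per kit less those lost or unused, it gives 5/6 = 83.3% and total is correct.

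**Step 4. Reach**
- Endpoints 6 and 7 use the symptom sum on Days 1–7, 11, 14 and 25 (SAP 7.9.3), and Days 1–6 come from the app. One woman-day is 1/26 = 3.8% of that day's data. The second sequence affects two woman-days: one empty and one scored earlier than intended.
- The symptoms in the primary endpoint's score are asked by the investigator at the visit and entered in the eCRF (SAP 6.4). The app rule does not touch them.

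**The case against.** **Relief already in the plan.** Forms started between 00:00 and 04:00 are moved back, and later ones can be on proof. This stands, and it rules out the reading that every morning-after form is misdated. But the proof clause is discretionary, has no criteria, and concerns only dating. It does nothing for a No followed by a Yes on the same evening.

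**Mandatory forms.** The full rule reads "In case of multiple assessments during the same study day (while also taking the mandatory forms into account), the first non-missing assessment will be used". The bracketed words could mean that scheduled forms have priority, and the dating sentence covers only patient-initiated forms. A scheduled form completed late may therefore be dated correctly; the SAP does not say. That limits the next-morning problem to patient-initiated forms. Priority for the mandatory form would not rescue a Yes if the mandatory form itself held the early No.

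**SAP 8.3 could mean any Yes.** Its wording allows that. But SAP 6.5 governs all analyses without exception, so the two sections need reconciling. A No also prompts a free-text reason, which might say that the dose was still to come, but no rule uses that text.

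**Small effect.** Largely right. Compliance is descriptive, and endpoints 6 and 7 carry estimates and intervals, not tests. If the symptom sum fell evenly from 6 to 1 over six days (an assumption), a form 15 hours early would be 5/6 × 15/24 = 0.52 points too high, or 0.52/26 = 0.02 on that day's mean. In these examples the errors lower compliance and delay apparent relief, so they do not favour the device.

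**Stronger readings.** A reader might infer that reported compliance as a whole is unreliable, or that mean patient-reported compliance falls by 3 × 100/26 = 11.5 points. The first ignores the maximum rule. The second needs three women to answer too early and correct themselves on all six days, and the documents give no frequency for such entries. Nor can an effect on the per-protocol set be computed: SAP 7.2.2 states no compliance threshold and leaves exclusions to the clean file meeting.

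**Conclusion.** The point holds in limited form. For the application question, SAP 6.5 as written keeps the wrong answer whenever a woman reports No before her dose and Yes after it on the same study day. A patient-initiated form started from 04:00 the next morning, without accepted proof, is dated to the new day. A Day 5 dose confirmed that way is not counted, and on Days 1–6 the form can displace that day's later symptom score.

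The size is 16.7 points of patient-reported compliance per dosing day lost, for the woman concerned. Total compliance is wrong only when the kit-derived figure is also below the true value. The conclusion rests on a literal reading of SAP 6.5 and on such entries occurring, at an unknown rate. The primary endpoint is not affected. This is a modest defect, worth correcting because the better rule is clear and costs almost nothing.

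**What to change.** 1. **Application question (SAP 6.5 and 8.3).** Count a dosing day as applied if any form tied to that dosing night says Yes. Include a next-morning form started before that day's dose when the previous night has no Yes. State the clock cut-off that defines next morning, and let one Yes count for one night only.
2. **Symptom scores (SAP 6.5).** A patient-initiated next-morning form must never displace that day's scheduled (mandatory) form when the latter is non-missing. A rule based on closeness to bedtime is not advised, because the questionnaire does not record bedtime.
3. **Late mandatory forms.** State which study day a mandatory form completed late belongs to.

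The cost is a few lines of SAP text and a small programming change using form start times, which SAP 6.5 already relies on. No new data are needed. The downside is that a few next-morning confirmations are credited to the previous night. If the database is already locked, the change belongs in the clinical investigation report as a documented deviation, as Protocol section 12 requires.

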6.5.1 Vaginal candidiasis symptoms and pessary administration

The following information will be collected in the ePRO system.

Pessary administration:

At Days 0 to 5, the patient should confirm that they have administered the pessary:

Question on treatment days:

Have you applied the pessary?

- Yes
- No

If no, please provide reason: (free text).

Scoring of vulvovaginal candidiasis symptoms:

The vulvovaginal candidiasis (VVC) symptoms will be rated by all patients on Days 0 to 6, Day 11 and Day 25.

The VVC symptoms will be rated according to 0-3 scale, as shown below.

	0 = none (absent)	1 = mild (slight)	2 = moderate (definitely present)	3 = severe (marked, intense)
Itching				
Burning				
Irritation				

Statistical Analysis Plan

Study ID: CL4

6.5.2 Usability

The below questions about usability will be filled in by all patients on Day 6.

1. Is the vaginal pessary easy to use?

- Yes
- No

If no, provide reason: (free text).

2. Did all pessaries remain in the vagina during treatment?

- Yes
- No

(if No) 2a. During how many dose administrations did you experience that the pessary did not remain in the vagina?

- Once
- 2-3
- 4-5
- All

2b. When the pessary does not remain, how would you describe what most frequently is happening?

- Just small pieces are falling out
- Large pieces are falling out

Please specify after how long time they generally falls out.

- Within 12 hours
- Between 12-24 hours after administration
- More than 24 hours after administration
- The whole pessary is falling out

Please specify after how long time it falls out.

- Within 12 hours
- Between 12-24 hours after administration
- More than 24 hours after administration

3. How do you generally regard the treatment?

1	2	3	4	5	6	7	8	9	10
Not satisfied					Very satisfied				

6.6 Microbiology assessment

Vaginal samples will be collected via a vaginal swab by the Investigator or delegatee on site visits (Day 0, Day 7 and Day 14) or by patients themselves at home, on Day 25.

The collected samples will be used for the following analyses.

- **Microscopic analysis; presence of hyphae:** KOH or saline test for fungus, using samples collected on Day 0, Day 7 and Day 14. Briefly, vaginal samples will be covered with 10% to 20% KOH, or 0.9% isotonic NaCl solution, and inspected under a microscope. Presence of hyphae

Study ID: CL4

- indicates Candida and will serve as an immediate, preliminary VVC diagnosis (present, absent, traced).
- **Candida culture:** Samples collected on Days 0, 7, 14 and 25, will be sent to laboratory for culture and confirmation of the VVC diagnosis/mycological cure. Vaginal swab culture result (positive, negative) and species present (C.albicans, C. tropicalis, C. glabrata, C. krusei, Other) will be recorded in the eCRF.
- **Sequencing of the vaginal microbiome:** Vaginal swabs for sequencing of the vaginal microbiome will be collected on Days 0, 7, 14, and 25. The effects of the investigational product on the vaginal microbiome will be assessed. Collected samples will be sent to a central laboratory for assessment of bacterial and fungus species, through DNA sequencing.

